Clinical Investigation Plan

CP341

Exploratory study investigating the acute effect of intermittent catheterisation on the bladder mucosa of healthy volunteers with a micro-hole zone catheter compared to a conventional 2-eyelet catheter.

Investigation period: December 2021 - March 2022

Document date: December 13 2021

CHANGE LOG

VERSION ISSUED BY NUMBER (INITIALS)		COMMENTS (MAJOR CHANGES SINCE LAST REVISION)			
1.0		Initial document created based on template			
2.0		Correct units for WBC and RBC labs.			
3.0		Updates to the endpoints and statistical sections.			

This confidential document is the property of Coloplast A/S. No unpublished information contained herein may be disclosed without written approval of Coloplast A/S.

SYNOPSIS OF THE CLINICAL INVESTIGATION

Title

CP341 / Exploratory study investigating the acute effect of intermittent catheterisation on the bladder mucosa of healthy volunteers with a micro-hole zone catheter compared to a conventional 2-eyelet catheter.

Test Product and Comparator:

The female test catheter is based on the current SpeediCath™ standard female catheter. The SpeediCath™ catheter has two oval holes by the tip used for voiding while the test catheter has a micro-hole zone comprising of a number of smaller holes by the tip, creating a draining zone. The hole punch process used for SpeediCath™ Standard, has been exchanged with a laser process to accommodate for the smaller hole size.

Hence, non-US approved test products will be investigated. The test product will be provided by Coloplast A/S, Denmark.

The comparator product is the Infyna Chic™ (Hollister) catheter, which is considered Standard of Care. The comparator product will be supplied by Coloplast A/S, Denmark.

Intended Purpose

The test product is a urinary catheter for bladder drainage through the urethra. The product is for intermittent use.

Aim and Objective(s)

The overall purpose of the clinical investigation is to explore the effect of micro-hole zone versus conventional catheter eyelets on bladder mucosa during catheterisation.

The primary objective is to show that a micro-hole zone catheter (MHC) causes fewer endoscopically noticeable epithelial and vascular changes in the bladder mucosa during catheterisation compared to a conventional 2-eyelet catheter (2EC).

Design of the investigation

This investigation is a randomized, single-blinded, parallel, single-center investigation. In total, up to 50 subjects (40 completers) will be included and each subject will have two test visits overseen by the Principal Investigator (PI), or designee. Each subject will be enrolled in the investigation, which can be up to 3 days (if Day 0 and Day 1 are not on same day). The subjects will be randomly assigned to test either the test product or the comparator product, with at least 20 subjects assigned to each product."

Expected duration of the clinical investigation:

The investigation will be conducted from November 2021 through February 2022.

Endpoints & Assessments:

Primary endpoint:

• Change in appearance of the bladder mucosa (pre- and post-catheterization) (Δ), rated on a 4-point scale following visit 2.

Exploratory endpoints:

- Haematuria red blood cell count (RBC) at visit 2.
- White blood cell count (WBC) at visit 2.

Assessments

- Visual blood at cystoscopes and catheter Yes/No
- Pre-catheterization residual volume (ml)
- Haematuria red blood cell count (RBC)
- White blood cell count (WBC)

Urine volumes (mL)

Safety assessments:

- Adverse events
- Device deficiencies
- Concomitant medications

Population/subjects

A total of 50 subjects (healthy female volunteers) will be recruited in order to secure inclusion, randomization and completion of at least 40 subjects, assuming an approximate drop-out rate of 20%." The subjects will be recruited from a single center, American Health Research (AHR).

Inclusion/Exclusion Criteria:

	be included in the investigation a subject must comply the the following inclusion criteria:	Justification for inclusion criteria			
1.	Has given written informed consent	To ensure that the subject has been given written and oral information regarding the investigation and know enough about the investigation to decide on participation.			
2.	Is at least 18 years and have full legal capacity	To meet the Helsinki Declaration			
3.	Is female	The product is indicated for use with females			
4.	Has a negative urine Multistix dipstick test for erythrocytes (haematuria)	Haematuria could be a sign of urinary tract infection (UTI).			

A:	subject is not allowed to participate in case he/she:	Justification for exclusion criteria:
1,	Has used an internal urinary catheter or cystoscopy within the past month	To reduce potential bias from other events non-distinguishable from this study
2.	Has prior history of bladder surgery	To reduce potential bias from other events non-distinguishable from this study
3.	Is symptomatic and/or on medication for overactive bladder	To reduce potential bias from other events non-distinguishable from this study
4.	Has evidence of ongoing, active, symptomatic UTI (assessed by PI, or delegate)	To reduce potential bias from other events non-distinguishable from this study
5.	Is pregnant and/or breast-feeding	To reduce potential bias from other events non-distinguishable from this study
6.	Is participating in other clinical investigations during this investigation	To reduce potential bias from other events non-distinguishable from this study
7.	Is menstruating during study period	To reduce bias of the RBC analysis.

Investigation approval

This investigation is a non-significant risk study and will be approved by the Institutional Review Board (IRB) before initiation.

LIST OF ABBREVIATIONS

ABBREVIATION	WRITTEN OUT	EXPLANATION
2EC	2-eyelet catheter	
ADE	Adverse Device Effect	See section 18.2
AE	Adverse Event	See section 18.1
ASADE	Anticipated Serious Adverse Device Effect	See section 18.4.2
CIP	Clinical Investigation Plan	5
CRF	Case Report Form (paper or electronic)	Questionnaire to be used for data collection
CM	Clinical Manager	
DD	Device deficiency	4
eCRF	Electronic Case Report Form	
IB	Investigator's Brochure	Compilation of the current clinical and non-clinical information on the investigational medical device(s,) relevant to the clinical investigation.
IFU	Instruction For Use	
ITT	Intention to Treat	
МНС	Micro-hole zone catheter	
PI	Principal Investigator	Qualified person responsible for conducting the clinical investigation at an investigation site. If the clinical investigation is conducted by a team of individuals at an investigation site, the PI is the responsible leader of the team. Whether this is the responsibility of an individual or an institution can depend on national regulations.
PP	Per Protocol	-
RBC	Red Blood Cell Count	e e
SADE	Serious Adverse Device Effect	See section 18.4.1
SAE	Serious Adverse Event	See section 18.4
USADE	Unanticipated Serious Adverse Device Effect	See section 18.4.3
UTI	Urinary Tract Infection	
WBC	White Blood Cell Count	

SIGNATURE PAGE

All parties declare by their signature on the electronic or the separate signature page to follow the Clinical Investigation Plan CP341 in accordance with the Declaration of Helsinki, ISO 14155, and FDA Regulations.

TABLE OF CONTENTS

1.2 Site Personnel

This clinical investigation will be conducted in the United States at a single-center, American Health Research, AHR.

The Clinical Manager is responsible for maintaining an updated list of all sites and personnel in the sponsor electronic trial master file (eTMF). Qualified site personnel can perform investigational related tasks per the Principal Investigator's (PI) delegation. This delegation must be documented in the 'Site Personal Signature and Delegation List' for each site. All PIs and designees will receive training in all aspects of the investigation and before they can begin any study related procedures.

1.3 Clinical Research Organizations

A Site Management Organization (SMO) will be used to help conduct the investigation as a clinical site. All sponsor representatives' roles and responsibilities will be listed on the 'Site Personnel and Contact Details List'.

1.4 Other Vendors

The data management system is delivered by Medidata Solutions and is named Rave. Current version number is version 2020 3.2. The system is designed for electronic data capture, and it is compliant with the requirements of 21 CFR part 11.

2 Rationale for conducting the clinical investigation

The hypothesis is that a catheter with multiple micro-holes will cause less mucosal suction through the eyelets during bladder emptying compared to a conventional 2-eyelet catheter and that suction can cause epithelial and vascular changes in the bladder mucosa.

[figure not shown]
3 Objective(s) of the clinical investigation

The overall purpose of the clinical investigation is to explore the effect of micro-hole zone versus conventional catheter eyelets on bladder mucosa during catheterisation. The primary objective is to show that MHC cause fewer epithelial and vascular micro-trauma in the bladder mucosa during catheterisation compared to a 2EC.

4 Investigational Products

4.1 Description of Test Product

The female test catheter is compositional identical to the 510K cleared (K180258) SpeediCath™ standard female catheter. The SpeediCath™ catheter has two oval holes by the tip used for voiding while the test catheter has a micro-hole zone comprising of a number of smaller holes by the tip, creating a draining zone. The hole punch process used for SpeediCath™ Standard, has been exchanged with a laser process to accommodate for the smaller hole size.

No of rows:	4
Hole size:	0,4mm
Distance between holes:	2,1mm
No of holes:	14x4

Hence, non-US approved test products will be tested. The test product will be provided by Coloplast A/S, Denmark.

4.2 Comparator

The comparator product is the Infyna Chic™ (Hollister) catheter, which is considered Standard of Care. The comparator product is already on the market and will be used within the intended purpose in this clinical investigation. The comparator will be supplied to the site by Coloplast A/S, Denmark.

4.3 Manufacturing

The Test Products will be manufactured at Coloplast A/S, [name].

The comparators are manufactured by Hollister.

4.4 Identification and traceability of the investigational products

All investigational products (test and comparator products) are labelled as per regulations and include "CAUTION – Investigational device. Limited by United States law to investigational use" on the label. The products are also identified with study number, product name/code, and item/lot number and accounted for through a master sponsor accountability log. Upon IRB approval, investigational products will be shipped to the principal investigator, or designee. Additionally, all investigational products will be accounted for and documented on a site accountability log. The receipt and disposition of all investigational products will be verified through monitoring. All unused products will be returned to Coloplast at the end of the study.

4.5 Intended use of the test product in the clinical investigation

The test product is a urinary catheter for bladder drainage through the urethra. The product is for intermittent use.

4.6 Intended population for the test product

The test product is indicated for use with adults.

4.7 Handling of the investigational products

The handling of the investigational products is described in detail in the Instruction for Use (IFU), which is included in all boxes with the products. It is stated in the IFU that the investigational products are for single-use and must be kept away from direct sunlight. Reprocessing, washing, disinfection, and sterilisation may compromise product characteristics, causing additional risk of physical harm to or infection of the user.

All site personnel will receive training by the sponsor and/or principal investigator in the handling and correct use of the investigational products.

For further details regarding the test product, please refer to the Investigators Brochure.

4.8 Total number of investigational products intended for the clinical investigation

The subjects will be included for up to 3 days. Subjects will undergo 1 catherization and expect to use up to 1 catheter.

5 Design of the clinical investigation

5.1 General

A randomized, single-blinded, parallel study, in which each subject will undergo one catheterization comprising of 6 cycles of filling and emptying the bladder. Each cycle will comprise of filling the bladder with 250mL of saline liquid (50mL/min) through the catheter, followed by bladder emptying through the catheter. The catheter will be rotated during emptying at each occurrence of a flow-stop to release any mucosal suction, with the MHC or 2EC, depending on randomization. To ensure that all catheters are rotated at some point during drainage, every catheter should be rotated after complete emptying. Subjects shall be sitting or standing for the catheterization and filling/emptying cycles to increase the efficiency of drainage.

Upon first insertion of the catheter, the residual volume pre-catheterization will be recorded to ensure minimal residual urine left in the bladder prior to the 6 cycles.

The effect of the micro-hole zone or conventional eyelets on the epithelial and vascular urothelial tissue will be assessed with cystoscopies before and after the catheterization including 6 cycles of filling/emptying/rotating.

One investigator will perform the cystoscopies, catheterizations, and make initial assessments of the cystoscopy images according to a 4-point rating scale as described in 5.3. Two additional investigators will evaluate the endoscopic images post-procedure in a blinded fashion. The evaluations by the 3 investigators will be compared.

The urine at pre- and post-catheterization at Visit 2will be collected for each subject, the total volume noted, and the container will be sent to a local lab for examination of microscopic RBC[1] and WBC results.

Each visit will take approximately 1-2 hours to complete.

Figure 5-1 presents the study overview and Table 7-1 presents the schedule of assessments.

[figure not shown]

Figure 5-1 Study overview

5.2 Investigation Endpoints

Endpoint details are included in the schedule of assessments. See section 7.4.

5.2.1 Primary endpoint

 Change in appearance of the bladder mucosa post- and pre-catheterization (∆), rated on a 4-point scale 1) no lesions evident; 2) minor mucosal and blood vessel lesions; 3) major blood vessel lesions, and 4) major mucosal and blood vessel lesions, following visit 2

5.2.2 Exploratory endpoints

- Haematuria red blood cell count (RBC) at visit 2
- White blood cell count (WBC) at visit 2.

5.2.3 Assessments

- Visual blood at cystoscopes and catheter Yes/No
- Pre-catheterization residual volume (ml)
- Haematuria red blood cell count (RBC)
- White blood cell count (WBC)
- Urine volumes (mL)

5.2.4 Safety assessments

- Adverse events
- Device deficiencies
- Concomitant medication

5.3 Rationale for selection and measurement of endpoints

Bladder lesions will be assessed with a cystoscope and graded by the principal investigator during the procedure, followed by a post-procedure evaluation of the images by two other specialised investigators in a blinded fashion.

Lesions are based on change in appearance of the bladder wall mucosa before and after catheterisation graded on a 4-point scale: 1) no lesions evident; 2) minor mucosal and blood vessel lesions; 3) major blood vessel lesions, and 4) major mucosal and blood vessel lesions. The change in the appearance of the bladder mucosa will be calculated by the difference between the grading of bladder lesions pre-catheterisation and post-catheterisations.

Figure 5-2 presents examples of changes in bladder mucosal grade observed pre- and post-drainage, from Grocela et al. 2010[2].

[figure not shown]

Figure 5-2 Examples of changes in bladder mucosal grade observed pre- and post-drainage, from Grocela et al. 2010[2]

RBC and WBC before and after catheterisation will serve as exploratory endpoint.

5.4 Demography and potential compromising factors

The following baseline data will be collected and registered at Visit 1 by the investigator or designee:

- · Date of Informed Consent
- Subject number
- Date of visit
- Age
- · Check of inclusion criteria
- Check of exclusion criteria
- Complete randomization

There are no restrictions. However, concomitant medication should be noted. Prophylactic antibiotics should be provided as one time treatment at first visit.

5.5 Equipment

The Ambu® aScope™ 4 Cysto is the cystoscope which will be used in this investigation. The aScope™ 4 Cysto is a sterile, single-use, flexible cystoscope intended to be used for endoscopic access to and examination of the lower urinary tract.

The Ambu® a View™ 2 Advance is a display unit used in conjunction with the cystoscopes in order to view the cystoscopy procedure.

5.6 Randomisation Procedure

All subjects that meet the eligibility criteria will be randomised to one of two treatment arms, the test product, or the comparator. Randomisation will be centralized using Medidata RAVE.

5.7 Blinding

Subjects will not be blinded during this investigation, as it is not possible to blind the products due to visible differences. The two investigators conducting the cystoscopy reviews will be blinded. The images will be deidentified and uploaded to a secure site. The images will be identified with a subject number, date, and time. The investigators will be provided access to the secure site for their review. Each investigator will grade both the post-catheterization image and pre-catheterization image, i.e., from the same location (grading is done in a comparative manner).

Any discordant gradings will be adjudicated amongst the investigators.

Additionally, the trial statistician will be blinded until database lock to ensure decisions related to data before database lock do not affect final results.

5.8 Total expected duration of the clinical investigation

The dates below are approximate, and no subjects will be enrolled before all required approvals have been obtained. If changes are required, applicable IRB will be notified.

- First subject enrolled (November 2021).
- Last subject completed (January 2022).
- Database Lock (February 2022).

Each subject participation will be approximately 3 days.

6 Clinical Investigation population

According to the sample size calculations (see section 10.4) 40 subjects are required to complete the study with measurements of the primary endpoint. Considering a drop-out rate of 20%, the required total number of subjects to be enrolled in the trial shall be 50. The subjects will be enrolled at one site in the United States.

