6.3 Point of Enrollment

A subject is considered enrolled in the investigation when written informed consent is obtained. The expected duration for each subject is described in section 5.8.

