10.4 Sample size

As this is an exploratory study no formal sample size calculation has been performed. It is assumed that a total of 40 completers i.e., 20 completers (a minimum of 18 completers needed) in each group (MHC and 2EC) will be adequate for obtaining indications on differences in eyelet associated trauma during bladder emptying with either a MHC or a 2EC.

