10.5 Level of significance and power

A two-sided significance level of 5% will be applied. For a description of the power see section 10.4 above.

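### Does the plan rest 40 completers on a calculation it never made, and does its floor of 20 assigned per product undercut its own minimum of 18 completers?

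*Combined protocol and SAP*

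**What the plan says.** Three places in the plan speak to the basis of the sample size.

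- Section 6, on the study population, states: "According to the sample size calculations (see section 10.4) 40 subjects are required to complete the study with measurements of the primary endpoint".
- Section 10.5 (Level of significance and power): "For a description of the power see section 10.4 above".
- Section 10.4 (Sample size): "As this is an exploratory study no formal sample size calculation has been performed". It then assumes that 40 completers will be adequate, namely "20 completers (a minimum of 18 completers needed) in each group (MHC and 2EC"). It states no power, effect size or standard deviation.

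The numbers to be recruited appear in the synopsis and in section 6.

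- The synopsis, under the design, allows up to 50 subjects for 40 completers and randomises them "with at least 20 subjects assigned to each product".
- The synopsis, under the population, recruits 50 "in order to secure inclusion, randomization and completion of at least 40 subjects, assuming an approximate drop-out rate of 20" per cent.
- Section 6: "Considering a drop-out rate of 20%, the required total number of subjects to be enrolled in the trial shall be 50".
- Section 6.3: "A subject is considered enrolled in the investigation when written informed consent is obtained".

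Section 5.6 randomises every eligible subject. Section 7.2.1 keeps screening failures out of the randomisation, and section 6.4 allows them to be replaced.

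**The concern.** There are two separate worries.

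The first is about provenance. A reader who stops at section 6 or section 10.5 will believe that the trial's size comes from a calculation with a stated power. The section they are sent to has neither. If a report repeated that claim, the study would look better founded than it is.

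The second is about units. The synopsis floor counts subjects assigned, whereas section 10.4 counts subjects who complete. Applying the plan's 20% drop-out to exactly 20 assigned leaves 16 expected completers, below the 18 that section 10.4 calls needed. On that view a group could satisfy the synopsis and still fall short of section 10.4, and the comparison of the two catheters would be less precise than intended.

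**Working it through.** **Inputs from the plan:** 40 completers in total, 20 per group, minimum 18 per group (section 10.4); drop-out of 20% and 50 enrolled (synopsis and section 6); floor of 20 assigned per product (synopsis). **Assumption:** equal allocation. The plan gives no ratio, but 20 completers in each group implies it.

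**1. The plan's own figure.** Enrolment = completers / (1 − drop-out) = 40 / (1 − 0.20) = 50. This reproduces. Per group it is 20 / 0.8 = 25. The 40 itself cannot be reproduced because no effect size, standard deviation or power is given. Section 10.4 says as much, so this is a disclosed assumption and not a failed calculation.

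**2. Where the 20% is counted.** The text allows two readings.

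| Reading | Randomised | Assigned per product | Expected completers per group |
|---|---|---|---|
| A: 20% is lost after randomisation | 50 | 25 | 25 × 0.8 = 20 |
| B: 20% covers all loss from consent onward, taken here as all at screening | 50 × 0.8 = 40 | 20 | 20 |

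Under A the floor of 20 assigned does not bind. Under B it is met exactly, and the 20% has already been used. Both arrive at section 10.4's target.

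**3. Where 16 comes from.** 20 × 0.8 = 16 combines the 20 per product of reading B with the later loss of reading A. From 50 subjects this leaves 50 × 0.8 × 0.8 = 32 completers, a loss of 1 − 0.64 = 36%. The plan assumes about 20%.

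**4. Chance of reaching the minimum of 18.** With independent losses, the chance in one group is P(Bin(n, 1 − l) ≥ 18), squared for both groups.

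| Loss after randomisation | 20 per group: expected completers | 20 per group: both reach 18 | 25 per group: both reach 18 |
|---|---|---|---|
| 5% (assumed) | 19 | 0.9245² = 0.855 | over 0.999 |
| 10% (assumed) | 18 | 0.6769² = 0.458 | 0.995 |
| 15% (assumed) | 17 | 0.4049² = 0.164 | 0.950 |
| 20% (the plan's figure) | 16 | 0.2061² = 0.042 | 0.8909² = 0.794 |

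The 20% row belongs with 25 per group (reading A). The low figure of 0.042 is the double-counted case of step 3.

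**5. What a small shortfall would cost.** As an illustration, with one value per subject, the 95% confidence interval half-width in SD units is t(0.975, 2n − 2) × √(2/n).

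- n = 20: 0.640
- n = 18: 0.677, which is 0.677 / 0.640 = 1.06 times as wide
- n = 16: 0.722, which is 0.722 / 0.640 = 1.13 times as wide

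**The case for a change.** The strongest case for a change is that nothing in the plan secures 25 per product. The 50 is a ceiling and is counted at consent, before eligibility is known. Screening failures may be replaced but need not be. No allocation ratio or blocking is written down. The assigned floor is then the only stated protection for each group, and it can be met while a group ends below 18. A 20/30 split, for example, respects both the floor and the total, and 40 completers could then divide 16/24.

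Part of this stands. The plan does not guarantee 18 per group, and it does not say where the 20% is counted. If screening takes the whole 20% and there is further loss, the margin is two subjects per group (18/20 = 90%).

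The rest is weaker. A 20/30 split needs unequal allocation, which sits badly with 20 completers in each group. The floor is not written as a stopping rule, and the completer target stands beside it in the synopsis, so meeting the floor does not release anyone from the target. The 18 triggers no analysis rule, and section 10.6 sets no pass/fail criterion. Randomising 25 per product would not guarantee 18 either: at 20% loss at least one group misses it with probability 1 − 0.794 = 0.206. If only about 40 were meant to be randomised, it could also put up to 50 − 40 = 10 more healthy volunteers through catheterisation and cystoscopy.

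On provenance, the objection is right about the text. The references in sections 6 and 10.5 lead to nothing of the kind they promise.

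**Conclusion.** No change to the plan follows.

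The cross-references in sections 6 and 10.5 are a clerical slip. Section 10.4 is the governing text, it discloses that the size is assumed, and it carries the same 40. Anyone writing the report would describe the size as assumed and claim no power.

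The floor of 20 assigned is compatible with 20 completers per group, since that many completers need at least that many assigned. Under either reading of the 20%, the plan's figures give 20 expected completers per group. The shortfall to 16 needs a 36% total loss that the plan does not assume. Where the 20% is counted is a missing detail that the site and the statistician can settle without altering the target or the analysis.

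This rests on equal allocation and, under the reading in which the 20% includes screening, on little loss after randomisation. If a group did end at 18, the interval would be about 6% wider than at 20, which is tolerable in a study meant to give indications.
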